15.4 Analysis of Secondary Endpoints

The analysis of the secondary endpoint to determine the efficacy of targeted naltrexone versus placebo in reducing alcohol-associated sexual risk behaviors, we will use GEE Poisson models with robust standard errors for the four monthly ACASI assessments on numbers of male anal sex partners, HIV-serodiscordant unprotected anal sex partners, unprotected anal sex partners while intoxicated with alcohol, and unprotected anal sex events with serodiscordant partners, including the baseline value. In the event that these outcomes are severely over-dispersed, we will analyze indicators for any self-report of each behavior, using GEE logistic models. **MDEs:** Based on estimates of within-subject correlation and control prevalence from our Project Echo trial, we estimate that the study will have 80% power to detect 31% reductions in numbers of male anal sex partners, 57% reductions in SDUA partners, 46% reductions in UA partners while intoxicated with alcohol, and 56% reductions in UA events with serodiscordant partners. In analyses using GEE logistic models, we will have 80% power to detect reductions of 14%, 38%, 39%, and 30% in any report of these four sexual risk behaviors, respectively.

Safety and tolerability data will be summarized by treatment group.

Adverse event rates will be coded by body system and MedDra classification term. Adverse events will be tabulated by treatment group and will include the number of patients for whom the event occurred, the rate of occurrence, and the severity and relationship to study drug.

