1 BACKGROUND

1.1 Overview of Overview of Clinical Studies

[figure not shown]
Binge drinking is a major health issue for men who have sex with men (MSM) at high-risk for acquiring or transmitting HIV. In the National HIV Behavioral Surveillance (NHBS) survey, 84% of MSM consumed alcohol in the past 30 days, and 57% reported at least one occasion of binge drinking.³ The prevalence of binge drinking for MSM is 3.5 times the prevalence in the general US adult population.¹ **The high rates of alcohol use in MSM have been observed for decades and these rates will likely persist.¹⁵⁻¹⁷** In San Francisco, 72% and 55% of MSM reported binge drinking in the past 12 months, and the past 30 days, respectively.¹⁸ Binge drinking is by far the most prevalent exposure attributed to HIV infections among MSM and it is estimated that there are 48,070 binge-drinking MSM in San Francisco.^{19, 20} **MSM are disproportionately impacted by HIV**, accounting for 61% of new infections in 2009.²¹ For San Francisco MSM, HIV prevalence is estimated at 22.7% and HIV annual incidence is estimated at 1.27% per year.²² It is imperative to develop more evidence-based HIV-prevention interventions that are not only efficacious, but also feasible and acceptable to MSM.

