6.2 Inclusion Criteria

- (1) Male gender;
- (2) self-reported anal sex with men in the prior three months while under the influence of alcohol;
- (3) at least one binge drinking (five or more drinks on a single occasion) session per week in the prior three months;
- (4) interested in reducing binge alcohol consumption;
- (5) HIV-negative by rapid antibody test or medical record documentation of HIV infection (HIV positive participants);
- (6) no current acute illnesses requiring prolonged medical care;
- (7) no chronic illnesses that are likely to progress clinically during trial participation;
- (8) able and willing to provide informed consent and adhere to visit schedule;
- (9) age 18-70 years;
- (10) baseline CBC, total protein, albumin, glucose, alkaline phosphatase, creatinine, BUN, and electrolytes without clinically significant abnormalities as determined by study clinician in conjunction with symptoms, physical exam, and medical history.
- (11) Written informed consent (and assent when applicable) obtained from subject or subject's legal representative and ability for subject to comply with the requirements of the study.

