8 STUDY TREATMENTS

8.1 Method of Assigning Subjects to Treatment Groups

The Better Than Study will enroll 120-participants for the double-blinded placebo controlled trial where 60 eligible participants will be randomly assigned to the treatment group receiving Naltrexone and 60 participants will be randomly assigned to the control group receiving placebo in a 1:1 ratio using a computer-generated randomization scheme developed by our biostatistician. The study biostatistician will generate a random allocation sequence list with treatment assignments associated with order of enrollment, using randomly permuted blocks with randomly selected block sizes.

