15.2 Demographic and Baseline Characteristics

The following demographic variables at screening will be summarized by treatment group: race, gender, age, educational attainment, employed, and HIV positivity.

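### The two serodiscordant-sex models should prespecify enrollment HIV status as a covariate beside the baseline value: a modest precision gain on secondary outcomes

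*Combined protocol and SAP*

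**What the plan says.** Section 15.4 (repeated in section 3.2 and in the synopsis under Specific Aim 3) analyses four sexual-risk outcomes by GEE Poisson with robust standard errors on four monthly ACASI assessments. Two of them count serodiscordant partners or "unprotected anal sex events with serodiscordant partners, including the baseline value". No other covariate is named. If the counts are severely over-dispersed, "we will analyze indicators for any self-report of each behavior, using GEE logistic models", again with no covariate named. The reductions stated as detectable with 80% power are 57% for serodiscordant partners and 56% for serodiscordant events.

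Both HIV statuses are eligible: inclusion criterion 5 in section 6.2 reads "HIV-negative by rapid antibody test or medical record documentation of HIV infection (HIV positive participants". Section 8.1 allocates 60 men to each arm "using randomly permuted blocks with randomly selected block sizes", and no stratification factor is named. HIV status appears in the statistical section only in the list of characteristics to be summarized by arm (section 15.2): "race, gender, age, educational attainment, employed, and HIV positivity". Section 15 adds that a detailed SAP will be written before the final analysis and may modify these analyses.

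**The concern.** A serodiscordant partner is one whose status differs from the participant's, so the same pattern of partners gives different counts for an HIV-positive and an HIV-negative man. Status is therefore a plausible fixed predictor of both outcomes, and it is already collected for everyone. One month's count before treatment is a noisy stand-in for it. Leaving status out of the model keeps avoidable variance in the two outcomes with the largest detectable reductions among the four Poisson outcomes. The section 15.2 table will also show any gap between arms in HIV positivity. Without a prespecified adjustment, the team would then have to leave the gap alone or adjust after seeing it.

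**Working it through.** **1. The plan's own figures.** The 57% and 56% cannot be recomputed, because the control means, over-dispersion and within-subject correlation are not given. Assuming the two-sided 5% level stated for Aims 1 and 2, they can be solved backwards: SE(log rate ratio) = −ln(1 − reduction)/(1.96 + 0.84).
- 57%: 0.844/2.80 = 0.301.
- 56%: 0.821/2.80 = 0.293.

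**2. How strongly status might matter.** Section 1.1 says "HIV prevalence is estimated at 22.7" per cent in San Francisco MSM. Under random mixing, a partner is discordant with probability 0.227 for an HIV-negative man and 0.773 for an HIV-positive man, a ratio of 0.773/0.227 = 3.4. Random mixing is an assumption, and so is using the city figure for the share of HIV-positive participants. I therefore take R, the HIV-positive to HIV-negative rate ratio, from 1 to 5.

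**3. Chance imbalance.** Take 27 of 120 men as HIV-positive (22.5%), 60 per arm. The number in one arm is hypergeometric with variance 60 × (27/120) × (93/120) × (60/119) = 5.27, SD 2.30. The SD of the difference in shares is 2 × 2.30/60 = 7.7 points. The exact chance of a gap of at least 10 points is 19%, and of at least 15 points 8%.

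**4. What a 10-point gap does with no covariate.** With shares of 27.5% and 17.5%, the rate ratio is multiplied by (1 + 0.275(R − 1))/(1 + 0.175(R − 1)):
- R = 2: 1.275/1.175 = 1.09.
- R = 3: 1.55/1.35 = 1.15.
- R = 5: 2.10/1.70 = 1.24.

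**5. What remains once the baseline count is a covariate.** This needs simulation. The set-up was 60 per arm, baseline plus three monthly gamma-Poisson counts, no treatment effect, no dropout, and each man HIV-positive with probability 0.227. Control means were 0.3 or 0.8 per month, with two over-dispersion patterns. The estimator was Poisson under working independence, with log(baseline + 0.5), with and without HIV status. None of these means or over-dispersion levels is in the documents.

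| R | SE change from adding HIV status | Power at 57% reduction | Shift per 10-point gap, baseline only |
|---|---|---|---|
| 1 | +0.3 to +0.6% | about 80% | about 0 |
| 2 | +0.3 to −1.7% | 80–81% | 5–7% |
| 3 | −1.5 to −5.7% | 81–84% | 7–12% |
| 5 | −4.1 to −6.7% | 83–85% | 13–17% |

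With HIV status also in the model, the shift is about zero (multiplier 0.98–1.02). Separate runs at R = 3.4 gave a standard error about 2–6% smaller, and at R = 1 at most 0.8% larger.

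The power column takes the stated 80% to refer to the baseline-adjusted model. Power is then Φ(0.844/(0.301 × SE factor) − 1.96). For R = 2 at best: 0.844/(0.301 × 0.983) − 1.96 = 0.89, power 81%. For R = 3 at best: 0.844/(0.301 × 0.943) − 1.96 = 1.01, power 84%. At the largest gain in the table (6.7%), the detectable reduction moves from 57% to 1 − exp(−2.80 × 0.301 × 0.933) = 54.5%.

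**6. The other reading of the baseline phrase.** ACASI is given at enrollment and at months 1, 2 and 3, so the four monthly assessments could include baseline as a response, with the effect read from an arm-by-time contrast. A fixed multiplier on a man's rate then raises baseline and follow-up alike and cancels. In simulation, adding HIV status as a main effect left the SD of the treatment estimate unchanged to three decimals. If the arms are instead constrained to a common baseline mean, the gain returns (about 1–8% of the standard error).

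**The case against.** The strongest reply is that the plan does not ignore status, because the baseline value of the same outcome already carries part of it. This stands, and it limits the size. A reader might compare a model containing HIV status with one containing no covariate at all. A simulation of that comparison at 54 per arm gave power rising from 81% to 87%, but the plan already includes the baseline value, so that gain is not on offer.

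A reader might also infer from the 3.4-fold figure that status largely determines these counts. The documents do not support that. The outcomes are unprotected partners and events, which reflect choice as well as chance. The documents do not say how partners of unknown status are counted, and no rate by status is reported.

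A third inference would be that an imbalance in HIV status could pass for a drug effect and so bias the trial. Under randomization, such imbalance is part of the sampling variance that the robust standard error already covers. It affects precision and the reading of the one realized result, not bias or the type I error rate.

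The reply that a main effect adds nothing when baseline is a response with an arm-by-time contrast is also correct. The text does not settle which reading is meant, so the fix has to settle it. Finally, in the logistic fallback an added covariate makes the odds ratio conditional on HIV status, so the change is not entirely free there.

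**Conclusion.** The point holds as a modest improvement to two secondary outcomes. Beyond the baseline covariate, adding HIV status is worth about 0–2% of the standard error at a 2-fold rate ratio and about 2–6% at 3 to 3.4-fold. That puts power at about 80–81% and 81–84% respectively at the stated 57% reduction. If status does not matter, the cost is under 1% of the standard error. These figures rest on assumed rate ratios, monthly means and over-dispersion, on 22.7% of participants being HIV-positive, and on the stated 80% referring to the baseline-adjusted model. Adjustment also removes the residual shift of roughly 5–12% (R of 2 to 3) that a 10-point gap in HIV positivity would leave in the realized rate ratio. The primary analysis is unaffected.

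**What to change.** In section 15.4 and synopsis Specific Aim 3:
- State that the baseline value enters as a covariate and that months 1, 2 and 3 are the responses.
- For serodiscordant unprotected partners and serodiscordant unprotected events, add enrollment HIV status (positive/negative) as a covariate.
- For the GEE logistic fallback, say whether the same covariates apply and, if so, that the odds ratio is conditional on HIV status.

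This takes two or three sentences and no new data, since status is already established for each man. The statistical cost is one degree of freedom in each model. It can be written into the detailed SAP that section 15 promises before the final analysis.

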STATISTICS Primary Analysis Plan	
We will use generalized estimating equations (GEE) to estimate treatment effects on repeated study outcomes. Primary analyses will be by intention-to-treat, without regard to adherence to treatment. In our prior trials, we had excellent retention and visit adherence. Nonetheless, in this high-risk population, missing data may be encountered.^{123, 124} We will conduct sensitivity analyses imputing all missing urine samples as positive, adjusting for baseline correlates of missingness, and using inverse probability of censoring weights.¹²⁵
 
Specific Aim 1: To determine the efficacy of targeted naltrexone versus placebo in reducing binge drinking among non-dependent MSM, as determined by number of binge drinking days in timeline follow-back (TLFB), by arm. GEE Poisson models with robust standard errors will be used to assess reductions on weekly drinking outcomes. Baseline TLFB results will be included in the analysis. Minimum detectable effects (MDEs): In calculating minimum detectable effects, we hypothesized on pharmacologic grounds that oral naltrexone will reach full efficacy against alcohol use almost immediately; accordingly we expect treatment-control differences to be approximately constant over the 12 weeks of the trial. Based on the prior trial (93% retention), we estimate that 90% of participants will be retained at 12 weeks. Using estimates based on data from Project ECHO⁹² for the within-subject correlation and over-dispersion of the outcomes, as well as the mean frequency among controls, we estimate that the proposed study will have 80% power in 2-sided tests with a type-I error rate of 5% to detect 27% reductions in numbers of binge drinking occasions, as well as 10% reductions in the average numbers of drinks on drinking days.
 
Specific Aim 2: To determine the efficacy of targeted naltrexone versus placebo in reducing alcohol consumption among non-dependent MSM, as determined by the proportion of ethyl glucuronide (EtG) positive urines, by arm. GEE logistic models with robust standard errors will be used to assess reductions frequency of positive urine tests, accounting for within-subject correlation. MDEs: Using the assumptions for loss to follow-up for Aim 1, as well as estimates based on biomarker data from Batki et al's study on Topiramate for alcohol use disorders¹²² for the within-subject correlation and control group urine positivity rate, we estimate that the study will have 80% power in 2-sided tests with a type-I error rate of 5% to detect 15-23% reductions in the urine positivity rate in the treatment arm.
 
Specific Aim 3: To determine the efficacy of targeted naltrexone versus placebo in reducing alcohol-associated sexual risk behaviors, we will use GEE Poisson models with robust standard errors for the four monthly ACASI assessments on numbers of male anal sex partners, HIV-serodiscordant unprotected anal sex partners, unprotected anal sex partners while intoxicated with alcohol, and unprotected anal sex events with serodiscordant partners, including the baseline value. In the event that these outcomes are severely over-dispersed, we will analyze indicators for any self-report of each behavior, using GEE logistic models. MDEs: Based on estimates of within-subject correlation and control prevalence from our Project Echo trial, we estimate that the study will have 80% power to detect 31% reductions in numbers of male anal sex partners, 57% reductions in SDUA partners, 46% reductions in UA partners while intoxicated with alcohol, and 56% reductions in UA events with serodiscordant partners. In

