---	--

	analyses using GEE logistic models, we will have 80% power to detect reductions of 14%, 38%, 39%, and 30% in any report of these four sexual risk behaviors, respectively.
Rationale for Number of Subjects	Given our estimate that there are 48,070 binge-drinking MSM in San Francisco ^{19, 20} and our prior trial enrollment rates, we are confident that we will be able to recruit 120 eligible non-dependent, binge-drinking MSM for the proposed trial.

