9.2 Other Clinical Procedures

9.2.1 Medical Management (MM) counseling for alcohol use:

This study's aim is to determine efficacy of a pharmacologic intervention to reduce binge drinking, against a background of relatively brief counseling that would be feasible in a clinical setting with limited resources. Thus, we will adapt a manualized version of the MM brief counseling platform used in NIAAA's COMBINE study.^{72, 105} In that trial, naltrexone with MM showed the most significant reductions in heavy drinking days (Hazard Ratio: 0.72; p=0.02) compared to 7 other treatment conditions.⁷² MM has been used in a targeted pharmacotherapy trial⁸¹ and our team has successfully used MM in alcohol pharmacologic trials. MM is a low-intensity supportive program designed to increase problem recognition and enhance motivation to change maladaptive alcohol use patterns. Participants will receive individual 20 minute MM sessions weekly from trained staff supervised by a clinical psychologist, with monthly quality assurance sessions.

9.2.2 Behavioral survey measurements:

Standardized and validated behavioral measures^{106-109, 111, 112, 115} will be assessed using audio computer administered surveys (ACASI) to minimize underreporting of risk activities and standardize data collection.^{106, 107} To minimize potential social desirability bias, staff will not have access to data during the trial.

9.2.3 Measures of adherence:

The study will collect self-reported adherence via weekly modified TLFB assessments, similar to prior targeted naltrexone studies^{11, 81} and via daily SMS text messages. Pill counts at weekly visits will also assess adherence. **MEMs cap dispensers** will be used to track medication adherence daily; each dispenser opening is recorded as a medication event in a remote database in real time. MEMs cap dispensers have been shown to be reliable for real time monitoring of medication adherence, even in resource-limited settings.¹¹⁷ We have had great success with electronic medical monitoring devices in prior studies among MSM.^{53, 84}

9.2.4 Ecological Momentary Assessments:

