10.3 Visit 3 (Enrollment Visit – month 1)

Assign randomization. You are assigned by a computer by chance to either thnaltrexone or placebo groups.

Collect urine to test for alcohol, opiates, and other substances.

If capable of becoming pregnant, we will collect urine and perform a pregnancy test. Provide study medication (naltrexone or placebo) in medical monitoring devices (“MEMS” containers). MEMS devices will record each time you open the container to retrieve a study medication capsule. Provided with a Wallet Card that explains that you may or may not be on a study medication (naltrexone or placebo). This card will provide the study clinician’s pager number who can provide information to other doctors in the event of an emergency. The card will also instruct the emergency room or other doctor providing treatment to provide information to the study clinician about the care they provide.

Collect blood sample to test for alcohol (PEth test).

Perform ACASI questionnaire on a computer.

Meet with counselor about alcohol consumption

Initiate Ecological Momentary Assessments

10.4 Visit 4 (weeks 1, 2, 3, 5, 6, 7, 9, 10, and 11))

Record any Adverse Experiences and dosing compliance by downloading MEMs cap dispenser.

Meet with the counselor regarding alcohol consumption and use of the study medication.

Collect urine sample to test for alcohol, opiates and other substances. If capable of becoming pregnant, we will also conduct a pregnancy test.

Answer ACASI questions on a computer

Receive the study medication: if needed, you will be given more of the study medication (except at the week 12 visit).

Meet with the study doctor or nurse: to talk about any problems with the study medication or any changes in your health or medications if needed. A physical exam may be done.

Collect a blood sample (weeks 3, 6, & 9): to test for alcohol. A few drops of blood will be collected by a lancet stick to your finger or a venipuncture blood draw.

10.5 Visit 5 (Month 1, 2 and 3 with visit window 2 weeks before visit and 2 weeks after visit)

All the same procedures as the weekly visits **PLUS** these additional procedures:

Answer ACASI questions on a computer about your mood, your recent sexual behavior and drug use, and your feelings about being in the study.

Record any Adverse Experiences and dosing compliance.

Record changes to concomitant medications.

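### The logistic fallback gives two different detectable reductions (38% and 30%) for what is, as the plan defines it, one yes/no outcome: any serodiscordant unprotected anal sex

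*Combined protocol and SAP*

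**What the plan says.** Section 15.4 lists four outcomes from the monthly ACASI assessments: the number of male anal sex partners, then "HIV-serodiscordant unprotected anal sex partners, unprotected anal sex partners while intoxicated with alcohol, and unprotected anal sex events with serodiscordant partners". The counts are to be analysed with GEE Poisson models, including the baseline value. If they are severely over-dispersed, "we will analyze indicators for any self-report of each behavior, using GEE logistic models".

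The Poisson figures name each outcome. The logistic figures follow in the same order, closed by the word respectively: "we will have 80% power to detect reductions of 14%, 38%, 39%, and 30% in any report of these four sexual risk behaviors, respectively". Set out together:

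| Outcome | Detectable reduction, count | Detectable reduction, any report |
|---|---|---|
| Male anal sex partners | 31% | 14% |
| Serodiscordant unprotected partners | 57% | 38% |
| Unprotected partners while intoxicated | 46% | 39% |
| Unprotected events with serodiscordant partners | 56% | 30% |

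The same figures appear in the synopsis (Specific Aim 3) and in Section 5.2. The stated source is the within-subject correlation and control prevalence from Project Echo; neither value is given.

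On measurement, Section 9.2.2 says that the behavioural measures "will be assessed using audio computer administered surveys (ACASI) to minimize underreporting of risk activities and standardize data collection". Section 10.5 has participants at the monthly visits "Answer ACASI questions on a computer about your mood, your recent sexual behavior and drug use". Neither section gives the wording of an item, a recall window or a skip rule.

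**The concern.** The second and fourth outcomes describe the same behaviour counted in two ways, by partner and by event. The counts can have different means, dispersion and correlation, so 57% against 56% raises no question. Once each is reduced to any or none, the distinction goes: a man with at least one serodiscordant unprotected partner has had at least one such event, and a man with at least one such event has had such a partner. One variable cannot have two detectable reductions at the same power in the same trial.

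These are the only power statements for the binary form of this aim. As written, a reader cannot tell whether the design detects a 30% reduction or only a 38% reduction in any serodiscordant unprotected anal sex. If both outcomes move to the fallback, two of the four results would also be one variable analysed and reported twice.

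**Working it through.** **1. Reproducing the stated figures.** This cannot be done, because the Project Echo prevalence and correlation are not in the documents. What can be tested is whether 38% and 30% can both hold for one variable.

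**2. Inputs.**
- 120 randomised 1:1, so 60 per arm (Sections 8.1 and 15.6).
- 90% retention, so 0.90 × 60 = 54 per arm; two-sided 5% test (Section 15.3). Both are stated for Aims 1 and 2 and assumed to carry over to this aim.
- 80% power (Section 15.4).
- k = 3 post-baseline assessments, or 4 if baseline is counted as an outcome.
- Exchangeable correlation ρ from 0.1 to 0.7 (assumption).

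**3. Formulas.** With control prevalence p0, reduction r, p1 = p0(1 − r) and q = 1 − p:
- Risk difference: power = Φ( (p0 − p1) / √[f(p0q0 + p1q1)/n] − 1.96 ).
- Log-odds: power = Φ( ln OR / √[f(1/(p0q0) + 1/(p1q1))/n] − 1.96 ), with OR the control odds over the treated odds.
- f = (1 + (k − 1)ρ)/k without the baseline value; subtract ρ² with it.

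The value of p0 is solved so that one stated reduction has exactly 80% power. The other reduction is then evaluated at that same p0. The solved p0 is a device for the comparison, not an estimate of prevalence.

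**4. Worked example (risk difference, n = 54, k = 3, ρ = 0.5, no baseline).** f = (1 + 2 × 0.5)/3 = 0.667.

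| Anchored at 80% | p0 | r tested | p1 | p0 − p1 | SE | Ratio | Power |
|---|---|---|---|---|---|---|---|
| 38% | 0.564 | 38% | 0.349 | 0.214 | 0.0764 | 2.802 | 0.80 |
| 38% | 0.564 | 30% | 0.394 | 0.169 | 0.0774 | 2.185 | 0.589 |
| 30% | 0.703 | 30% | 0.492 | 0.211 | 0.0753 | 2.802 | 0.80 |
| 30% | 0.703 | 38% | 0.436 | 0.267 | 0.0749 | 3.564 | 0.946 |

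Power is Φ(ratio − 1.96). If 38% is right, 80% power for 30% would need (2.802/2.185)² = 1.64 times the analysed sample.

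**5. Full grid.** 56 cases: n 54 or 60, k 3 or 4, ρ 0.1 to 0.7 in steps of 0.1, with and without baseline.

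| Scale | Power for 30% if 38% has 80% | Power for 38% if 30% has 80% | Sample ratio |
|---|---|---|---|
| Risk difference | 0.583–0.591 | 0.944–0.950 | 1.64–1.67 |
| Log-odds | 0.589–0.605 | 0.933–0.947 | 1.58–1.64 |

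**6. Rounding.** The closest values that still round to the stated figures are 37.5% and 30.5%. The two powers become 0.610–0.618 and 0.932–0.938 (risk difference), and 0.616–0.631 and 0.921–0.934 (log-odds). The gap remains.

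**7. Other readings.** If both figures are taken as reductions in odds with equal standard errors, the powers are 0.552 and 0.964. A separate check with a pooled-variance two-proportion formula gives about 0.59 and 0.94. There, at 54 per arm and k = 3, the control prevalences needed for 38% and for 30% are 0.507 and 0.649 (ρ 0.3), 0.574 and 0.712 (ρ 0.5), and 0.629 and 0.761 (ρ 0.7). One indicator cannot have both prevalences.

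**The case against.** The strongest reply is that the figures rest on Project Echo items that nobody can see from these documents. The fallback analyses self-reports. Answers to separate partner and event questions need not agree, because of different wording, recall windows, skip rules or item non-response. A broader event item with a higher prevalence would give just this pattern, and then 38% and 30% could both be right. Sections 9.2.2 and 10.5 are silent on item wording, so they do not prove that the items match, and they describe this trial's survey rather than the source trial's. The power calculations assume a shared prevalence; they measure the gap if the indicators coincide and are not evidence that they do.

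All of that stands, and it is why the conclusion is conditional. It does not remove the point. As the plan names the two outcomes, they are equivalent once dichotomised, and nothing in it says that the items differ. If they do differ, the plan needs to say how, because a reader cannot otherwise interpret two results for one behaviour.

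It is also fair that the consequence is small: these are planning figures for a conditional analysis of a secondary aim. They do not set the sample size of 120 or change the conduct of the trial.

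**Conclusion.** The concern holds. On the plan's own definitions the two any-report indicators are one variable and must have one detectable reduction; the plan gives 38% and 30%. Unless the source items differed in a way the plan does not state, at least one figure, or the order of the four figures, is wrong. The documents do not show which.

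The logical point needs no numerical assumption. Its size does: it rests on the retention, test level and sidedness borrowed from Aims 1 and 2, and on exchangeable correlation. Across both scales, the power at the other stated reduction is about 58–61% or 93–95%, depending on which figure is taken as correct. Confidence is medium because the Project Echo inputs are not shown. Priority is low.

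**What to change.** Check the four logistic figures and their order against the Project Echo inputs. Then:

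- **If the two items are the same**, state one detectable reduction for any unprotected anal sex with a serodiscordant partner. When both outcomes move to the fallback, analyse and report that indicator once.
- **If the items differ**, state the difference in definition, recall window or skip logic, and keep both figures.

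Make the change in the synopsis, Section 5.2 and Section 15.4, and carry it into the detailed SAP that Section 15 promises. The over-dispersion fallback itself can stay. The sample ratio of about 1.6 to 1.7 only shows the size of the gap; it is not a reason to change the sample size.

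The cost is one check of the source-trial inputs, at most one recalculation, and wording changes in three places. Design, sample size and data collection are unaffected.
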